	2 nd	Diary	Last visit before the safety closeout visit
	3 rd	Max (SV last visit end date, “last visit” from eCRF)	SV last visit end date
	4 th	If no study drug exposure (FAS not SAF) use SV last visit end date	
		Reference end date will finally be replaced by maximum of reference start date and reference end date.	
TP start date	1 st	eCRF (TP1: reference start date) Exception 6/2 regimen: split protocol planned TPs with 168 days, assign start and end dates of these with CRF collected for planned TPs and derived start and end dates of split TPs.	TP1: reference start date TPs will be defined as consecutive 84-day time intervals starting with the date of randomization.
TP end date (excluding last TP)	1 st	eCRF exception 6/2 as above	
TP end date (last TP)	1 st	Reference end date	

eCRF = electronic case report form; EoT = end of treatment; SV=subject visit; TP = treatment period; VPR = vilaprisan

Treatment period

For subjects in treatment groups A1, A2, and A3, each treatment period (TP) consists of three subsequent 28-day periods. In case of premature discontinuation of study drug the last 28-day period of the respective treatment period might be shorter than 28 days. If a subject took the study drug for more than 84 days of a treatment period, the respective treatment period will be longer than 84 days, in contrast. Subjects treated in 3/1 and 3/2 regimens, have the first break after TP 1. Subjects treated in 6/2 regimens have two planned TPs before the first break.

The definition of TP here described which will be used in the analysis, differs from the definition of TP used in the protocol and Section 3 to describe the 6/2 treatment regimen. The definition used in the analysis allows for a better comparison between treatment regimens and is consistent with the reporting of other studies of the VPR project.

The first TP starts with the reference start date, the last TP ends with the reference end date. Start and end of a TP will be identified based on eCRF entries (EXCATN=1).

In 6/2 regimen, the protocol plans for TPs with 168 days each. The CRF only collects start and end dates of these protocol planned TPs.

For the analysis, the planned protocol TPs are split into 2 Analysis TPs:

- The first Analysis TP is assigned first available odd TP number and ends with day 84 (or the maximum number of available days if less than 84 days are reported).

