- The second Analysis TP is assigned the next higher even TP number, starts with day 85 and ends with the last day reported in the original protocol TP, even if this exceeds a total of 168 days.

For example, protocol TP1 = analysis TP1 + analysis TP2. Protocol TP2 = analysis TP 3 + analysis TP 4 etc.

If the original planned protocol TP is less than 85 days, no such second evenly numbered Analysis TP will be assigned. As a result of this a subject in 6/2 regimen might have Analysis TP 1, TP 3 and TP 4, but no Analysis TP 2.

If the end date of the current treatment period is equal to the start date of the next treatment period based on CRF entries, it is assumed that the current treatment period ended one day earlier. The end date of the current treatment period is therefore moved back by one day.

For all TPs excluding the last TP, in case end of TP date is still missing, it will be replaced by the date of the last study drug intake within the respective TP according to diary (EXCATN=5 and EXMEDN>=1).

Subjects in treatment group B don't have any breaks. In the treatment group B TPs will be defined as consecutive 84-day time intervals starting with the date of randomization.

Replacement rules for missing end date of the last TP are analogue to those described for reference end dates.

TPs will be numbered sequentially.

Time intervals

Due to the complex visit schedule of the studies, a time-interval based approach is chosen to present data over time. Therefore, time intervals are defined which are used for different analysis topics.

The selection of time intervals used for a certain analysis topic will be described within each section.

An overview of the time intervals is given in [Figure 4-1](#).

Figure 4-1: Time interval overview

BL/Post baseline	Post baseline																										
Intervals A	Treatment Phase																		FUP Phase								
Intervals B	TP1 + BR1						TP2 + BR2						TPx						FUP1+2			FUP ...					
Intervals C	TP1			BR1			TP2			BR2			TPx			FUP1			FUP2			FUP ...					
Intervals D	BL	BL	BL	TP1	TP1	TP1	BR1	BR1	BR1	TP2	TP2	TP2	BR2	BR2	BR2	TPx	TPx	TPx	FUP	FUP	FUP	FUP	FUP	FUP	FUP	FUP	FUP
	1-28	29-56	57-x	1-28	29-56	57-84	1-28	29-56	...	1-28	29-56	57-84	1-28	29-56	...	1-28	29-56	57-84	1-28	29-56	57-84
AE Intervals	Pre-treatment			"on" (TP1 + 8d)			"off"			"on" (TP2 + 8d)			"off"			"on": TPx + 8d			"off"			Post-treatment (Start: day 61 after EoT)					

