All information available at the time of analysis will be included. For example, for a subject allocated to treatment group A1 (3/1 regimen) in subgroup 1 who completed the full planned treatment, the number of bleeding days will be counted from the 1st day of TP1 until the date when a new TP would theoretically start following the end of TP4 and the required bleeding episode that follows TP4, without gaps. If a subject withdrew while receiving treatment in TP3, the number of bleeding days will be considered from the 1st day of TP1 until the date when a new TP would theoretically start following the end of TP3 and the required bleeding episode that follows TP3, irrespective of the length of the incomplete TP3.

For subjects who did not start the next planned TP, due to the study being temporarily paused or any other reasons, as described in the section 'Break period', a theoretical end of break period will be derived in these cases. The number of bleeding days will be counted until the derived end of break period.

The period for evaluation of "number of bleeding days" for the treatment group B starts on the reference start date and ends on the reference end date. A theoretical end of break period following the reference end date will not be generated.

The analysis of the number of bleeding days from these pre-determined evaluation periods will be normalized to 28 days and 365 days.

Onset of amenorrhea for analysing time-to-event data

Onset of amenorrhea is defined by the first day for which the menstrual blood loss (assessed by MP) for all subsequent 28-day periods up to the end of the treatment period is <2 mL. Amenorrhea status will be assessed for each of the subsequent, overlapping 28-day periods within a treatment period. The censoring mechanism is assumed to be non-informative and the subjects will be handled as right-censored, if applicable. If a subject completed the 84 days of a treatment period and did not experience an onset of amenorrhea, the subject will be censored on Day 57 of the treatment period.

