For prematurely discontinued subjects, censoring also depends on whether an onset of amenorrhea can be ruled out or not during the time the subject was in the respective treatment period. An onset of amenorrhea can be ruled out, if in the last 28-day period before the subject discontinued the respective treatment period, the sum of MP values exceeds 2 mL. If this is not the case, then an onset of amenorrhea cannot be ruled out for the respective treatment period. Thus, there are in principle the two possibilities:

1. In case the subject discontinued the respective treatment period prematurely and an onset can be ruled out, subjects will be treated as right-censored at the first day of the last 28-day period after which MP bleeding values for all further days are missing.
2. If the subject prematurely discontinued the respective treatment period but an onset cannot be ruled out, the subject will be censored on the day before the first day of the first 28-day period which indicates that an onset may have taken place.

Onset of controlled bleeding

Defined by the first day for which the menstrual blood loss (assessed by MP) for all subsequent 28-day periods up to the end of the treatment period is <80 mL. The first 28 days with non-missing MP values until the last 28 days with non-missing MP values under treatment in the respective treatment period will be considered for deriving the time to onset of controlled bleeding. Time to onset of controlled bleeding is derived in the same way as time to onset of amenorrhea. The only difference is the use of a less strict criterion (i.e. <80 mL instead of <2 mL).

Start of bleeding after last study drug intake (assessed by UF-DBD)

Defined by the first day for which bleeding intensity is “mild” or higher after the last study drug intake. If no start of bleeding after last study drug intake is documented,

- Subjects will be censored at latest available date from the UF-DBD.
- If bleeding has to be induced, the subject’s data will be censored at the time point of bleeding induction. The bleeding induction information will be obtained from the concomitant medication page.
- For the analyses after last study drug intake in TP_x, the subject will be censored at latest at TP_{x+1} start date if she starts TP_{x+1}, where x=1,..., n.

Largest fibroid

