6.2.3.2 Time to event related variables

- Time to onset of amenorrhea for each treatment period
- Time to onset of controlled bleeding for each treatment period
- Time to start of bleeding after last study drug intake (assessed by the UF-DBD).

Time to event related variables and censoring rules are defined in [Section 4.5](#).

Time to onset variables will be analyzed using the Kaplan-Meier estimates (including number of events, number of censored, 25th, median, and 75th percentiles). This analysis will be performed using the calendar time (days) as unit. Kaplan-Meier plots will also be presented. The analysis will be done by treatment group and TP (time intervals B according to [Figure 2](#), excluding screening and FUP). For treatment group A2, TP per 168-day defined in the protocol will be used and shown separately.

Time to start of bleeding after last study drug intake for treatment group B will not be analyzed.

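### The fixed Day 57 censoring rule suits only 84-day treatment periods; in longer ones, including the 168-day A2 periods, it biases the Kaplan-Meier onset curves upward after Day 57

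*SAP*

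**What the plan says.** SAP Section 4.5 defines onset of amenorrhea as the first day from which menstrual blood loss "for all subsequent 28-day periods up to the end of the treatment period is <2 mL", using overlapping 28-day windows. The search for onset therefore runs to the end of the period, however long it is. For a subject who completed 84 days, the rule is that if she "did not experience an onset of amenorrhea, the subject will be censored on Day 57 of the treatment period".

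Premature discontinuers have their own rules in the same section. Where onset can be ruled out, they are "right-censored at the first day of the last 28-day period" with diary data. The method carries over to the second endpoint: "Time to onset of controlled bleeding is derived in the same way as time to onset of amenorrhea", with 80 mL in place of 2 mL.

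Periods are not always 84 days. If study drug is taken for longer, "the respective treatment period will be longer than 84 days". The second half of an A2 course "ends with the last day reported in the original protocol TP, even if this exceeds a total of 168 days". For the time-to-onset analysis, Section 6.2.3.2 states: "For treatment group A2, TP per 168-day defined in the protocol will be used and shown separately". The required output is Kaplan-Meier plots and estimates, "including number of events, number of censored, 25th, median, and 75th percentiles".

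**The concern.** The event definition follows the length of the period; the censoring day does not. In a period longer than 84 days, a completer without onset is taken out at Day 57 because of what happened after Day 57, namely that no onset came by the end of the period. That is informative censoring, although Section 4.5 assumes that censoring is non-informative. After Day 57 the risk set keeps every subject who will go on to have onset and drops the completers who will not, so the error can only be upward.

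The rule also sits badly with the one for discontinuers. If an A2 stop on Day 150 counts as premature and onset is ruled out, that subject stays at risk to Day 123, while a subject who completes 168 days without onset is removed at Day 57.

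At stake are the part of the curve after Day 57 and any percentile not reached by then, for amenorrhea and for controlled bleeding.

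**Working it through.** **Last possible onset day.** Onset must start a full 28-day window inside the period, so the last possible day is L − 28 + 1, where L is the period length.

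- L = 84: 84 − 28 + 1 = 57. This reproduces the SAP's figure.
- L = 90: 90 − 28 + 1 = 63.
- L = 150 (the Day 150 stop): 150 − 28 + 1 = 123.
- L = 168: 168 − 28 + 1 = 141.

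**Effect in a 168-day A2 period.** The SAP gives no onset rates, so these splits are assumptions: 100 subjects, 60 with onset by Day 56, late onsets evenly spaced over Days 58 to 140, and the rest completing without onset. Under either rule S(57) = 0.40. As written, only the late onsets remain at risk after Day 57, so S falls to 0 at the last of them. With censoring at Day 141, S ends at 0.40 × never/40.

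| Late / never | As written | Censored at Day 141 |
|---|---|---|
| 0 / 40 | 60% | 60% |
| 1 / 39 | 100% | 1 − 0.40 × 39/40 = 61% |
| 5 / 35 | 100% | 1 − 0.40 × 35/40 = 65% |
| 10 / 30 | 100% | 1 − 0.40 × 30/40 = 70% |

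**Percentiles, 10/30 case.** As written, at the fourth late onset (Day 85), S = 0.40 × (1 − 4/10) = 0.24 ≤ 0.25, so the 75th percentile is Day 85. With Day 141 it is not reached, because S never falls below 0.30. The 25th percentile and median are the same under both rules. The median can also be affected: in a separate example with 200 subjects, 40% with onset by Day 57, 5% later (evenly spaced over Days 60 to 141) and 55% never, it is Day 69 as written and not reached under the corrected rule.

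**With late discontinuers.** Keep 10/30, but let some of the 30 be discontinuers censored on Day 140, with the last onset on Day 135.

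- 5 discontinuers: as written S = 0.40 × 5/15 = 0.133, giving 86.7%.
- 10 discontinuers: as written S = 0.40 × 10/20 = 0.20, giving 80.0%.
- Corrected rule, both cases: S = 0.40 × 30/40 = 0.30, giving 70.0%.

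**A prolonged A1 period.** Assume 100 subjects: 55 onsets by Day 56, one on Day 59 in a longer period, and 44 without onset, of whom 10 had 90-day periods.

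- As written: S = 0.45 × 0/1 = 0, giving 100%.
- Corrected: the ten stay at risk to Day 63, so S = 0.45 × 10/11 = 0.409, giving 59.1%.

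**Exact 84-day periods.** Both rules censor on Day 57, so nothing changes.

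**The case against.** The best defence is that the Day 57 sentence was written for 84-day periods only. Section 4.5 builds analysis periods from three 28-day blocks and splits each A2 course at Day 84, and in that setting Day 57 is exactly right. On this reading the SAP states no biased rule. But it then has no censoring rule for A2 subjects who complete 168 days, or for prolonged periods, in an analysis that Section 6.2.3.2 requires. Either reading needs a correction.

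The sizes can also be challenged. Section 3 records that, under Amendment 9, A2 subjects in the first 84 days of a course were to finish only the first three months. A non-onset subject who stops at Day 84 is correctly censored on Day 57. If, as an assumption, 15 of the 30 non-onset subjects in the 10/30 case did so, the corrected estimate is 1 − 0.40 × 15/25 = 76%, and the gap to 100% shrinks from 30 to 24 points. The number of such subjects is not in the SAP. The 100% figures also need at least one late onset and nobody censored after the last one. These points limit the size; they leave the direction unchanged.

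An A2 subject who stops between Day 85 and Day 167 could fall under the discontinuer rule instead, so not every non-onset A2 subject need be censored on Day 57. That is fair, but the SAP does not say which rule governs such a stop.

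**Conclusion.** The concern holds. Followed literally, the rule biases cumulative onset upward after Day 57 in any period longer than 84 days, for both onset endpoints. In the assumed A2 examples with late onsets, the final estimate is 80% to 100% as written against 61% to 70% under the corrected rule, and one late onset can be enough to take the curve to 100%. With no onset after Day 57 there is no bias. Estimates up to Day 57 are unaffected, as are exact 84-day periods such as those defined for group B. The true size depends on late-onset rates and A2 stopping patterns that the SAP does not give. These are descriptive other-efficacy variables with A2 shown separately, so no test or primary result depends on them. The plan should be corrected because the affected curves and 75th percentiles are required output.

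**What to change.** For both onset endpoints, replace the fixed Day 57 with the first day of the last evaluable 28-day window of the treatment period. With complete diary data this is the last day of the period minus 27: Day 57 for 84 days and Day 141 for 168 days. It also agrees with the existing rule for discontinuers in whom onset is ruled out. Define evaluable as having non-missing pictogram values, so that the rule has one meaning when values are missing at the end of the period.

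Also state whether A2 subjects who stop between Day 84 and Day 167 are completers or premature discontinuers in the 168-day analysis. This still matters after the first change: a subject whose last windows meet the criterion has an event if she is a completer, but is censored under the SAP's second discontinuer rule if she is not.

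The cost is two sentences in the SAP and a small programming change. No new data are needed, and results for exact 84-day periods do not change.

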The baseline menstrual cycle length is defined as the days from the first day of cycle until the last day of cycle. First day of the baseline cycle is Day 1 of the bleeding episode following screening Visit 1. Last day of cycle is the day preceding the next bleeding episode. This definition will apply, if during this cycle the inclusion criterion of HMB diagnosis is fulfilled (menstrual blood loss > 80 mL). If HMB is not confirmed in the first bleeding episode following screening Visit 1, then the second bleeding episode will be considered. Similarly, the first day of the second cycle is the Day 1 of the second bleeding episode following screening Visit 1 and the day preceding the next bleeding episode will be considered the last day of the cycle. Again, this second bleeding episode will be considered the baseline cycle only if the HMB criterion is fulfilled, otherwise the next bleeding episode, if recorded, will be inspected for the diagnosis of HMB. If none of the bleeding episodes preceding the first drug administration/ reference start date fulfill the HMB inclusion criterion, the first bleeding episode following screening Visit 1 will be considered for the baseline cycle. If no such bleeding episode exists, the bleeding episode already ongoing at screening Visit 1 will be considered for the baseline cycle, starting with Day 1.

During the screening period the diagnosis of HMB will be inspected using the definition of bleeding episode based on the MP, as explained in this subsection and in the protocol. In contrast, during the analysis only the definition of bleeding episode based on the UF-DBD will be used. Therefore, the

baseline cycle defined during the analysis here described is independently derived and may differ from the bleeding episode used to assess the HMB diagnosis during the screening period.

Bleeding episode (assessed by the UF-DBD)

Bleeding episode is defined as day(s) with bleeding/spotting of which at least one day is of intensity “mild” or higher, preceded and followed by at least 2 days with diary entry: “no vaginal bleeding” (in case the first bleeding episode starts directly after Visit 1, the preceding 2 bleed-free days may not be recorded for this first bleeding episode).

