This definition of bleeding episode, based on the UF-DBD, is the only bleeding definition implemented in the analysis to identify bleeding episodes. The protocol includes a definition of bleeding episode based on the MP, which will be implemented during the screening period to facilitate the assessment of the HMB inclusion criterion (criterion 4, MBL >80 mL) by clinical sites. This latter definition of bleeding period will not be used in the analysis.

Menstrual blood loss for 28 days

Menstrual blood loss for 28 days is defined as the sum of menstrual blood loss [mL] by MP in a 28-day period. Non-overlapping 28-day periods will be created along the different study periods: TPs, break periods (if applicable), and FUP phase. In case of premature discontinuation of study drug the last 28-day period of the respective treatment period might be shorter than 28 days. For details about the volume of MBL assigned to MP, see Appendix 4.

Volume of menstrual blood loss per bleeding episode after the reference end date

Volume of menstrual blood loss for a bleeding episode is the sum of volume of menstrual blood loss [mL] data by MP in the respective episode after the reference end date.

Amenorrhea (defined as < 2 mL during last 28 days of treatment course) assessed by MP method

Amenorrhea is defined as menstrual blood loss less than 2 mL during the last 28 days of the respective treatment period. For missing data replacement please refer to section 4.3.

- i) the sum of the non-missing (i.e. original or imputed) MP values is ≥ 2 mL, or
- ii) there is at least one day with missing MP value and bleeding intensity of “mild” up to “very severe” after having applied the imputation rules, or
- iii) the subject did not complete at least 8 weeks of treatment.

If neither of i), ii) or iii) applies, the subject will be considered as having amenorrhea.

The last days under treatment with 28 days with non-missing (i.e. original or imputed) MP data will be used to calculate whether amenorrhea occurred. Thus, if the last 28 days of treatment include days with missing MP data, the left margin of this interval will be displaced backwards in time and step-wise until the required number of 28 non-missing values are included.

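### Time to start of bleeding after the last study drug intake counts a bleed already under way as a start on day 1

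*SAP*

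**What the plan says.** The entry for start of bleeding in SAP section 4.5 opens "Defined by the first day for which bleeding intensity is" and sets mild as the lowest qualifying intensity. That sentence closes, and the lead-in to three censoring bullets follows, with the words "or higher after the last study drug intake. If no start of bleeding after last study drug intake is documented". The bullets are:

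- censor at the last available diary date;
- if bleeding has to be induced, the "data will be censored at the time point of bleeding induction";
- a bullet opening "For the analyses after last study drug intake in TP", which censors at the latest when the next treatment period (TP) starts.

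The same section defines a bleeding episode, first by intensity: "Bleeding episode is defined as day(s) with bleeding/spotting of which at least one day is of intensity" at or above the mild threshold. It then asks for a clear interval on both sides, in that the episode must be "preceded and followed by at least 2 days with diary entry" showing none. The SAP says this definition "is the only bleeding definition implemented in the analysis to identify bleeding episodes". The start-of-bleeding rule does not use it.

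Section 6.2.3.2 analyses the variable by Kaplan-Meier, by treatment group and TP, reporting numbers of events and censored subjects, the 25th and 75th percentiles and the median. Group B is excluded.

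**The concern.** The variable is named as a start, and a continuing bleed is not one. Under the rule as written, two women with the same interval to their next bleed get different values if one of them was bleeding on her last tablet day: she is scored on day 1 and the other on the day bleeding returns.

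The plan expects such women. It provides for TPs that are stopped early, and it tabulates absence of bleeding in the last 28 days of a TP as an outcome that some will not reach. Its other off-drug measures work by episode: the theoretical end of a break is set by bleeding episodes, and blood loss within a break (section 6.2.3.1) is summed by episode, with explicit provision for episodes that cross the edge of the break.

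At stake is the description of how soon bleeding returns off drug. Early events that are not returns lower the reported percentiles, most of all the 25th.

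**Working it through.** The SAP states no figure for this variable, so there is none to reproduce. The check applies the rule to constructed diaries and then sizes the effect under stated assumptions.

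**1. Does another rule remove ongoing bleeding?** The only day-level exclusion in section 4.5 is for bleeding on the day of an endometrial biopsy and the 3 days after. It does not cover this case.

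**2. Constructed diaries**

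| Diary | Rule read literally | Censoring bullets read as caps | Caps plus new bleed required |
|---|---|---|---|
| Bleeding (mild, moderate, moderate) up to and including the last tablet day; then moderate, mild, mild, spotting; 24 bleed-free days; new bleed | event, day 1 | event, day 1 | event, day 29 |
| No bleed; induction on day 60; bleed on day 70 | event, day 70 | censored, day 60 | censored, day 60 |
| No bleed at last tablet; new bleed on day 28 | event, day 28 | event, day 28 | event, day 28 |

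Only a new-bleed condition corrects the first diary. The second depends solely on how the bullets are read.

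**3. Size of the ongoing-bleeding effect.** Let *p* be the share bleeding at last intake and *F* the distribution of time to a new bleed, assumed the same for all women. The rule as written puts the share *p* at day 1, so the reported quantile *q* solves

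p + (1 − p)·F(t) = q, that is F(t) = (q − p)/(1 − p).

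Neither *p* nor *F* is in the SAP. Two assumed forms of *F*:

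- lognormal, median 22 days, log-SD 0.5, so t = 22·exp(0.5·z) with z the normal quantile of F(t). With p = 0 the 25th percentile is 22·exp(0.5 × −0.6745) = 15.7 days;
- Normal, mean 30, SD 8 days, rounded to whole days, simulated with 20,000 subjects. With p = 0 the 25th percentile is 25 and the median 30.

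| p | Quantile | F(t) | Lognormal: days (shift) | Normal: days (shift) |
|---|---|---|---|---|
| 5% | 25th | 0.20/0.95 = 0.211 | 14.7 (−1.0) | 24 (−1) |
| 5% | median | 0.45/0.95 = 0.474 | 21.3 (−0.7) | 29 (−1) |
| 10% | 25th | 0.15/0.90 = 0.167 | 13.6 (−2.1) | 22 (−3) |
| 10% | median | 0.40/0.90 = 0.444 | 20.5 (−1.5) | 29 (−1) |

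At 20% the Normal case gives a 25th percentile of 18 and a median of 27 days. By the formula, the 25th percentile reaches day 1 only once p is at least 25%.

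**4. Size of the induction ambiguity.** Normal case, no ongoing bleeding, induction assumed at day 60 and the induced bleed at day 70. With 5%, 10% and 20% induced, all three quartiles agree under both readings (26, 33 and 42 days at 20%). Events are 100% under the literal reading and 95%, 90% and 80% when induction censors. The quartiles do not move because induction falls after the 75th percentile.

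**The case against.** **Induced bleeds.** Because the bullets hang from the lead-in about no documented start, a reader might infer that the SAP scores induced bleeds as spontaneous return. The documents do not support that. The induction bullet itself orders censoring at induction and names the data source. Needing induction presupposes that no start has been documented by then. The next-TP bullet makes sense only as a cap. What stands is ambiguous drafting that two programmers could code differently.

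**Any single mild day.** A reader might also think that counting one isolated mild day is wrong. It is not: with 2 bleed-free days on each side, that day is a bleeding episode under section 4.5. The gap is only the missing condition that the bleed be new.

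**A 25th percentile of day 1.** This would need at least 25% of a treatment group bleeding at last intake in a TP. Such a share might be imagined among TPs stopped early for bleeding, but section 6.2.3.2 does not analyse that subset separately, so its share does not carry over to the reported percentile.

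**Low stakes.** The variable is descriptive, has no test and no group B comparison. The primary variable (lumbar spine BMD) and the secondary efficacy variable (number of bleeding days) do not use this rule. This stands in full and limits the weight of the point. It does not make day 1 a correct value for a woman whose bleeding did not start then.

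**Conclusion.** The point holds for bleeding ongoing at the last intake. The rule as written gives such women an event on day 1 and loses their true return, under either reading of the censoring bullets. The bias is downward. With 5% to 10% ongoing it is about 1 to 3 days on the 25th percentile and about 0.7 to 1.5 days on the median. These sizes rest on assumed shares and assumed return-time distributions, since the SAP supplies neither; the direction does not.

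The placement of the induction and next-TP bullets is a matter of wording. Under the assumptions tried it affects event and censoring counts and the late tail, not the quartiles. No conclusion on the primary or secondary variables changes.

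**What to change.** Amend the entry in section 4.5 in two places.

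1. **Event.** Define it as the first mild-or-higher day after the last study drug intake that does not belong to a bleeding episode which already had a mild-or-higher day on or before that intake. A new bleed needs the 2 preceding days of no vaginal bleeding from the existing episode definition. The 2 bleed-free days afterwards should not be required here, so that a bleed still running when the diary ends is not lost.
2. **Censoring.** Take the induction and next-TP bullets out of the lead-in condition. Censor at the earlier of induction and next-TP start whenever it precedes the first such day, whether or not a later bleed is recorded.

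Keep the mild-or-higher threshold. Using Day 1 of the first new episode instead would look simpler, but that day may be spotting only, which would date events earlier. It would also drop a woman with spotting on her last tablet day that becomes mild on day 2: her episode was already open, yet bleeding of the required intensity began afterwards. Under the wording above she has an event on day 2.

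The cost is two sentences and a small programming change. The diary entries and the induction records from the concomitant medication page are already collected.
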